7.1.1 Screening Examination

All subjects will undergo an entry examination to evaluate their health status and their eligibility for inclusion in the study. The Screening examination will be conducted not more than 21 days prior to the planned first drug administration, ie between Day -21 to Day -2 before commencing to first study period. Only subjects who meet the inclusion criteria and none of the exclusion criteria will be admitted to the trial.

Prior to Screening examination, the subjects will receive a screening number for identification. Eligible subjects will receive a random number upon enrollment into the study.

There is a notification on the subject's card as well as in the electronic subjects' data base on the last participation in a trial. In addition, all subjects are reported to a central checking organization (VIP Check) before inclusion into the trial.

Prior to any Screening examinations the subjects must sign the informed consent form. This Screening examination will consist of the following:

- Demographic information including body height, body weight and BMI
- Medical history
- Physical examination
- Vital signs (supine blood pressure, pulse rate, and body temperature)
- 12-lead ECG
- Blood and urine samples for safety laboratory assessments

- Serological tests for hepatitis B, C, and HIV1/HIV2
- Serum pregnancy test for women
- Urine drug screen (including test for cotinine) and an alcohol breath test
- Prior medication and concomitant medication
- Assessment of AEs
- Preliminary evaluation of inclusion and exclusion criteria.

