7.4.1.2 Methods of Recording and Assessing Adverse Events

At each trial visit, the subject will be queried on changes in his or her condition. During the reporting period, any unfavorable changes in the subject's condition will be recorded as AEs, whether reported by the subject or observed by the Investigator.

Complete, accurate and consistent data on all AEs experienced for the duration of the reporting period (defined below) will be reported on an ongoing basis in the appropriate section of the eCRF. All SAEs must be additionally documented and reported using the appropriate Report Form as described in Section 7.4.1.4.

It is important that each AE report include a description of the event, its duration (onset and resolution dates and times when it is important to assess the time of AE onset relative to the recorded treatment administration time), its severity, its causal relationship with the trial treatment, any other potential causal factors, any treatment given or other action taken, including dose modification or discontinuation of the IMP, and its outcome. In addition, serious cases should be identified and the appropriate seriousness criteria documented.

Specific guidance can be found in the eCRF Completion and Monitoring Conventions.

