7.4.1.3 Definition of the Adverse Event Reporting Period

The AE reporting period for safety surveillance begins when the subject is initially included in the trial (date of first signature of informed consent) and continues until the End of Trial Visit.

Any SAE assessed as related to the IMPs must be reported whenever it occurs, irrespective of the time elapsed since the last administration of IMPs.

7.4.1.4 Procedure for Reporting Serious Adverse Events, Adverse Events of Special Interest and Dose Limiting Toxicities

Serious Adverse Events

In the event of any new SAE occurring during the reporting period, the Investigator must immediately (within a maximum of **24 hours** after becoming aware of the event) inform the Sponsor or its designee in writing. All written reports should be transmitted using the SAE Report Form, which must be completed by the Investigator following specific completion instructions.

In exceptional circumstances, an SAE (or follow-up information) may be reported by telephone; in these cases, a written report must be sent immediately thereafter by fax or e-mail. Names, addresses, and telephone and fax numbers for SAE reporting will be included in the trial-specific SAE Report Form.

Relevant pages from the eCRF may be provided in parallel (for example, medical history, concomitant drugs). Additional documents may be provided by the Investigator, if available (for example, laboratory results, hospital report, autopsy report). In all cases, the information provided on the SAE Report Form must be consistent with the data about the event recorded in the eCRF.

The Investigator must respond to any request for follow-up information (for example, additional information, outcome, final evaluation, other records where needed) or to any question the Sponsor/designee may have on the AE within the same timelines as those noted above for initial reports. This is necessary to ensure prompt assessment of the event by the Sponsor or designee and (as applicable) to allow the Sponsor to meet strict regulatory timelines associated with expedited safety reporting obligations.

Requests for follow-up will usually be made via the responsible Monitor, although in exceptional circumstances the Global Drug Safety department may contact the Investigator directly to obtain further information or to discuss the event.

Adverse Events of Special Interest

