7.4.4.3 Physical Examination

The physical examination comprises general appearance, skin, head, neck (including thyroid), eyes, ears, nose, throat, abdomen, as well as neurological, peripheral vascular, musculoskeletal, cardiovascular and pulmonary system.

Physical examination will be scheduled according to the study flow chart (see Table 1, Table 2 and Table 3). Further physical examinations during the course of the trial are at the discretion of the Investigator. Any relevant findings are to be recorded on the Medical History form in the eCRF (for findings from the past that occurred prior to ICF signature) or on the AE form in the eCRF (for findings presently occurring; events existing but unresolved prior to drug administration).

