## **15.1 Adverse Events**

The number and percentage of subjects experiencing at least one TEAE will be summarized by treatment as well as the number of events. A TEAE is an AE with onset after start of treatment. Tables by relationship to trial drug and by severity will be generated. AEs will be coded using Medical Dictionary for Regulatory Activities terminology, latest version.

Incomplete TEAE-related dates will be handled as follows:

- In case the onset date is missing completely or missing partially but the onset month and year, or the onset year are equal to the start of trial treatment then the onset date will be replaced by the minimum of start of trial treatment and TEAE resolution date.
- In all other cases the missing onset day or missing onset month will be replaced by 1.
- Incomplete stop dates will be replaced by the last day of the month (if day is missing only), if not resulting in a date later than the date of subject's death. In the latter case, the date of death will be used to impute the incomplete stop date.
- In all other cases the incomplete stop date will not be imputed.

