### **15.1.1 All Adverse Events**

All AEs recorded during the course of the trial (ie, assessed from signature of informed consent until the end of the Follow-up/End of Trial visit) will be coded according to MedDRA latest version and assigned to a SOC and PT.

TEAEs will be summarized by worst severity, using MedDRA latest version preferred term as event category and MedDRA primary system organ class (SOC) body term as Body System category. The severity of AEs will be graded using the “National Cancer Institute - Common Terminology Criteria for Adverse Events” (NCI-CTCAE) guideline, as detailed in the study protocol.

TEAEs related to trial treatment are those events with relationship missing, unknown or related.

The following will be summarized in an overview table with the number and percentage of subjects (and the number of events) by treatment and overall:

- Any TEAE
- Any trial treatment related TEAEs
- Any TEAE related to omeprazole
- Any TEAE related to tepotinib
- Any serious TEAEs

- Any trial treatment related serious TEAEs
- Any omeprazol related serious TEAEs
- Any tepotinib related serious TEAEs
- Any severe TEAE (grade  $\geq 3$ )
- Any trial treatment related severe TEAE (grade  $\geq 3$ )
- Any omeprazol related severe TEAE (grade  $\geq 3$ )
- Any tepotinib related severe TEAE (grade  $\geq 3$ )
- Any TEAEs leading to death
- Any trial treatment related TEAEs leading to death
- Any omeprazole related TEAEs leading to death
- Any tepotinib related TEAEs leading to death

TEAEs will be summarized by treatment and overall in tables with:

- The number and percentage of subjects by treatment with at least one TEAE and the number of events overall and by SOC and PT. Group/SOC terms will be sorted alphabetically and PTs within each group/SOC term will be sorted by descending frequency.
- The number and percentage of subjects by treatment with at least one non-serious TEAE and the number of non-serious TEAE applying frequency threshold of 5%. Group/SOC terms will be sorted alphabetically and PTs within each group/SOC term will be sorted by descending frequency.

In addition the following tables will be provided. Group/SOC terms will be sorted alphabetically and PTs within each group/SOC term will be sorted by descending frequency (based on all treatment groups combined):

- A table by severity of TEAEs with the number and percentage of subjects by treatment with at least one TEAE and the number of events by SOC and PT.

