- A table by relationship to trial treatment with the number and percentage of subjects by treatment with at least one TEAE and the number of events by SOC and PT.

Pre-treatment AEs (AEs with onset after informed consent but before start of treatment) and TEAEs will be listed separately.

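### SAP 15.1 defines a TEAE by onset alone, so an AE that began before the first dose and worsens in grade afterwards is missing from the TEAE tables if the worsening stays on its original record (optional, low impact)

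*SAP*

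**What the plan says.** The SAP gives the only definition of the term, in section 15.1: "A TEAE is an AE with onset after start of treatment". Section 15.1.1 applies the same split to the listings: "Pre-treatment AEs (AEs with onset after informed consent but before start of treatment) and TEAEs will be listed separately". The severity summary covers only events already classed as treatment-emergent: "TEAEs will be summarized by worst severity". The protocol uses the term in 8.3.2 and 8.5.4 without defining it, so it adds nothing on worsening.

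On collection, Protocol 7.4.1.3 says that the AE reporting period "begins when the subject is initially included in the trial (date of first signature of informed consent". Protocol 7.1.1 places the Screening examination "not more than 21 days prior to the planned first drug administration". Protocol 7.4.4.3 sends current physical examination findings to be entered "on the AE form in the eCRF (for findings presently occurring; events existing but unresolved prior to drug administration".

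On recording, Protocol 7.4.1.2 says that unfavorable changes in the subject's "condition will be recorded as AEs, whether reported by the subject or observed by the Investigator". For detail it refers elsewhere: "Specific guidance can be found in the eCRF Completion and Monitoring Conventions". Those conventions are not among the documents.

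**The concern.** A definition based on onset alone gives the right answer for an event that is new after dosing. It gives a doubtful answer for one that was present at a low grade before dosing and becomes worse on drug. Such a worsening is a change under treatment, and a safety summary should show it.

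Under the SAP as written, whether it is shown depends on how the site records it. A new record with a post-dose onset is counted. A higher grade entered on the existing record is not. Incidence, intensity and causality of TEAEs are part of a stated secondary endpoint (Protocol 8.3.2), so the rule should sit in the SAP.

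**Working it through.** The plan states no figure on this point, so there is none to reproduce. The check sets the rules side by side and then scales one misclassified subject.

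**1. Can an AE be open at the first dose?** Collection starts at consent, and Screening can be up to 21 days before the first dose, so there is time for an AE to begin. Inclusion criterion 5 bars only clinically significant abnormalities and disorders, at Screening and on Day -1. Paracetamol is permitted before dosing (exclusion criterion 14). A minor complaint therefore does not exclude a subject. Protocol 7.4.4.3 provides a place to record a finding that is unresolved before dosing.

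**2. What happens if its grade rises after dosing?**
- *New record:* the onset is after start of treatment, and SAP 15.1 counts the event as a TEAE.
- *Same record:* the onset remains before treatment, and SAP 15.1.1 lists the event with the pre-treatment AEs.

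**3. Which outputs lose it in the second case?** The any-TEAE, related and Grade 3 or higher rows of the overview table, the tables by severity and by relationship (SAP 15.1.1), and the summary and listing of TEAEs leading to discontinuation (SAP 15.1.2).

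**4. Which outputs would still show part of it?**
- The SAE table (SAP 15.2.2) is not restricted to TEAEs, and Protocol 7.4.1.1 requires clinical Grade 4 or 5 events to be reported as SAEs.
- The AESI listing (SAP 15.2.3.1) covers lipase and amylase elevations of Grade 3 or higher.
- The laboratory shift tables (SAP 15.3) compare discharge with pre-dose within each period.
- The QTcF change categories (SAP 15.5) do not use AE onset.
- The disposition table (SAP 10.1) counts discontinuations for an adverse event.
- The pre-treatment AE listing (SAP 15.1.1) contains the record itself.

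What can be missed is mainly a non-serious symptomatic worsening, which would be listed but would enter no TEAE count by treatment.

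**5. Size per affected subject.** Shift in one treatment's incidence = 1 / (subjects in the Safety Analysis Set on that treatment).
- 12 subjects as planned: 1/12 = 8.3 percentage points.
- 13 subjects: 1/13 = 7.7 points.
- 14 subjects: 1/14 = 7.1 points.

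The larger denominators can occur because drop-outs with incomplete PK data are replaced (Protocol 5.5.1 and 5.5.2), while a dosed drop-out with a later safety assessment stays in the Safety Analysis Set (SAP 8.2). The shift arises only if the subject has no other TEAE in the same table row.

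**6. Expected number.** The documents do not say how often an AE is open at the first dose. Taking 0 or 1 affected subject as an assumption, the shift is 0 to about 8 points for one treatment. No upper bound is claimed.

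**The case against.** The strongest objection is that Protocol 7.4.1.2 already closes the gap. A grade increase is an unfavorable change, and such changes are to be recorded as AEs. The ordinary reading may be a new record with a post-dose onset, which SAP 15.1 then counts. The same section asks for onset, resolution and severity per AE and mentions no date of grade change within a record. This is a fair reading and the reason the point is only conditional. It does not remove the point, because the section does not clearly require a new record and leaves the detail to conventions that are not supplied. Protocol 7.4.1.6, under which AEs are assessed continuously and for final outcome at the End of Trial Visit, fits a single record followed over time equally well.

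A reader might infer from Protocol 7.4.4.3 that the protocol expects AEs to be open at dosing. It does not show that. The sentence directs findings to one form or another, so it allows for an unresolved finding without saying that such subjects are dosed. Subjects must be healthy at Screening and on Day -1, and eligibility is rechecked on Day -1 of Period 1 (Protocol 5.4). Only minor events can be open.

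A reader might also infer that an AE which starts in one period and worsens in the next is lost. On the natural reading, start of treatment is the first dose in Period 1, so an AE that begins in a later period or a washout is already a TEAE. What is missing there is a rule for assigning the worsening to a treatment. That matters because the tables are by treatment, and any added clause must deal with it.

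It is also fair that the trial is descriptive, with no hypothesis tests (Protocol 8.1), and that 8.3 points is simply one subject in 12.

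**Conclusion.** The point holds in conditional form and at low weight. SAP 15.1 states an onset-only rule that can misclassify a post-dose worsening, and neither document supplies a worsening clause. The misclassification occurs only if the site keeps the grade increase on the original record. The documents do not support the reading that worsenings will routinely be lost.

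The likely effect is nil or one subject, about 8 percentage points of one treatment's TEAE incidence with 12 subjects. This rests on two assumptions: that 0 or 1 subject is affected, and that this subject has no other TEAE in the same row. An optional improvement is the right rating.

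**What to change.** In SAP 15.1, keep the present sentence and extend it: *or an AE present before start of treatment that increases in NCI-CTCAE grade after start of treatment; a worsened AE is assigned to the treatment of the period in which the grade increase occurred.*

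At the data review meeting already planned before database lock (SAP 6), go through the AEs open at the first dose and query the date of any grade increase that is not recorded. Without that date the event cannot be assigned to a treatment.

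The cost is one clause, a short check at an existing meeting and an occasional data query. TEAE counts may become slightly higher. If the eCRF conventions already require a new record for a worsening, the clause changes no count and only makes the rule explicit.

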### General Specifications for Data Analyses

Statistical analyses will be performed using the computer program package SAS® System for Windows™ (Version 9.4 or later; SAS Institute, Cary, North Carolina, USA).

The results of this trial will be reported using summary tables, figures, and data listings, as appropriate. All data will be summarized by treatment and/or scheduled time point, as appropriate.

For demographic, baseline and safety assessments, continuous measurements will be summarized by means of descriptive statistics (ie, number and percentage of observations, number and percentage of missing observations, mean, standard deviation [SD], median, Q1 and Q3, minimum, and maximum) and categorical data will be summarized by means of frequency tables (ie, count and percentages), if not stated otherwise. Mean, Median, Q1, Q3, Min, Max will have the same precision as the SDTM data (decimal places). SD will be presented with one decimal place more than the mean. For subject disposition and demographic tables the denominator will be the number of subjects in the analysis set. Counts of missing observations will be included as a separate category.

If not otherwise specified, ‘baseline’ refers to the last scheduled measurement before administration of the first drug in each period. However, if a subject is missing the baseline

collection, the previous non-missing evaluation within the same period predose could become the baseline value. If no baseline or previous to baseline evaluations exist then the baseline value will be treated as missing.

The following calculations and derivations, as applicable, will be used:

- Change from baseline: post-baseline visit value - baseline value
- Duration of AE (in days hh:mm) = end date and time - start date and time of the AE, if missing time for either the beginning or end then = end date – start date + 1
- Days hh:mm from dosing = start date and time of the event - date and time dose administration; (for treatment-emergent AEs), if missing time for either the dosing or event then = event start date – date of dose administration + 1
- Rel. Day in study of AE = start date of the event – date of First Admin + 1 (for AEs on or after the day of dosing)
- Rel. Day in study of AE = start date of the event – date of First Admin (for pre-treatment AEs only)

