## **15.3 Clinical Laboratory Evaluation**

All laboratory data will be reported with SI units. Laboratory parameters will be listed by subject and time-point and summarized indicating the treatment at the respective time-point using descriptive statistics for absolute values and change from baseline over time.. Data listings of abnormalities as per the NCI-CTCAE guideline will be provided. Shift tables for laboratory tests will be presented by treatment. Shift tables will be based on NCI-CTCAE grades, where possible, and on normal ranges otherwise. They will be produced for

- End of Trial versus Screening
- Discharge versus Pre-dose (Tepotinib administration) within periods.

Laboratory values that are outside the normal range will also be flagged in the data listings, along with corresponding normal ranges and NCI-CTCAE grade and will additionally be listed separately.

See section 7.4.3 of the clinical study protocol for a table of the safety laboratory evaluations.

Safety laboratory values are separated into:

- Hematology
- Biochemistry
- Urinalysis
- Other tests

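### In this three-period crossover, SAP 15.1 can date an incomplete AE onset to an earlier treatment, and SAP 15.3 lists End of Trial versus Screening shifts for display by treatment

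*SAP*

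**What the plan says.** SAP 15.1 defines treatment emergence without reference to a period: "A TEAE is an AE with onset after start of treatment". If the onset date is wholly missing, or its known parts agree with the month and year (or the year) of treatment start, it "will be replaced by the minimum of start of trial treatment and TEAE resolution date". For the rest, "In all other cases the missing onset day or missing onset month will be replaced by 1". SAP 15.1.1 then states that "TEAEs will be summarized by treatment and overall in tables with" counts by system organ class and preferred term. No sentence says how an event is assigned to a period or a treatment.

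For laboratory data, SAP 15.3 says "Shift tables for laboratory tests will be presented by treatment" and lists two contrasts. One is "End of Trial versus Screening"; the other compares discharge with the value before the tepotinib dose, within each period.

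Other parts of the SAP do work by period. In the general specifications (section 9), baseline "refers to the last scheduled measurement before administration of the first drug in each period". The same section counts the relative study day of an AE from the first administration in the trial ("date of First Admin + 1").

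**The concern.** Every subject receives all three treatments, so a by-treatment safety table means something only if each finding can be tied to a period. The onset rule carries only one treatment start for the whole trial, and the End of Trial contrast covers the whole trial.

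Safety and tolerability of tepotinib alone and with omeprazole is a secondary objective (Protocol 4.2). With 12 subjects, one event in the wrong column is visible. An End of Trial shift table split by treatment would also invite a comparison that the data cannot support.

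**Working it through.** **Inputs.** Tepotinib is given on Day 1 of Treatment A and on Day 5 of B and C, with omeprazole from Day 1 in B and C (Protocol 6.2). Tepotinib doses are at least 14 days apart (Protocol 5.1). There are six sequences with two subjects each (Protocol 8.2). The End of Trial Visit is 7 ± 1 days after the last tepotinib dose (Protocol 5.1), and screening starts up to 21 days before first dosing. The planned trial period is Q2-Q3 2018 (Protocol synopsis).

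**Timeline.** Count days from the first drug administration. A period starts on its tepotinib day for A, and 4 days before its tepotinib day for B and C. For A-B-C, tepotinib falls on days 0, 14 and 28, so periods start on days 0, 14 − 4 = 10 and 28 − 4 = 24. End of Trial is day 28 + 7 = 35.

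| Sequences | Period starts | End of Trial | Screening to End of Trial |
|---|---|---|---|
| ABC, ACB | 0, 10, 24 | 35 | 21 + 35 = 56 days |
| BAC, CAB | 0, 18, 28 | 39 | 21 + 39 = 60 days |
| BCA, CBA | 0, 14, 32 | 39 | 21 + 39 = 60 days |

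The last column reproduces the synopsis figure of about 2 months per subject.

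**Onset wholly missing, or month missing.** With the trial planned inside 2018, the onset year equals the treatment-start year, so the onset goes to the first dose. Taking the minimum with the resolution date can only move it earlier, never into a later period. Days 0 to End of Trial number 36, 40 and 40 in the three rows. Of these, 26, 22 and 26 lie in Periods 2 and 3: 74/116 = 64%. With an assumed 21-day washout the share is (33 + 29 + 33)/(50 + 54 + 54) = 95/158 = 60%. An onset on any of those days would be dated to Period 1 or before.

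**Only the day missing.** I read the year-only match as applying when the month is also unknown.

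- First-dose month: A-B-C first dosed on 1 June starts Period 2 on 11 June and Period 3 on 25 June. An onset in June with the day unknown becomes 1 June, under Treatment A, even if it began under B or C.
- Later month: A-B-C first dosed on 20 June starts Period 2 on 30 June and Period 3 on 14 July. A true onset on 20 July with the day unknown becomes 1 July, under B instead of C.

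Running through all six sequences and every first-dose date that lets the subject finish between April and September 2018 gives these shares of on-trial days:

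| Washout | Days in first-dose month: share, of which wrong period | Days in later months: share, of which wrong period | All days in wrong period |
|---|---|---|---|
| 14 days | 42.4%, 31.8% | 57.6%, 61.5% | 0.424 × 0.318 + 0.576 × 0.615 = 49% |
| 21 days (assumed) | 31.4%, 12.9% | 68.6%, 53.9% | 0.314 × 0.129 + 0.686 × 0.539 = 41% |

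These are shares of days, assuming onset is equally likely on each day. They are not expected numbers of events.

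**Size per event.** The tables count subjects with at least one event. One misplaced event therefore changes a treatment's incidence by at most 1/12 = 8.3 percentage points. It changes nothing in a column where that subject already has another qualifying event.

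**End of Trial versus Screening.** Each subject has one value of this contrast. By that visit a completer has had three tepotinib doses and 5 + 5 = 10 omeprazole doses. Placing each subject in all three columns gives three identical columns. Placing each under the last treatment gives 2 sequences × 2 subjects = 4 per column, all also exposed to the other two treatments. Neither display isolates a treatment.

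**The case against.** Much of the SAP is already period-based: baseline, change from baseline and the discharge shift. A complete onset date is untouched by the imputation rule. Subjects are resident until 72 h after tepotinib and then seen daily to 144 h, and AE reports must carry onset dates (Protocol 7.4.1.2), so incomplete dates should be rare. The SAP does not say that treatment is derived from the imputed date, and for the End of Trial shift it names no treatment column. The whole analysis is descriptive. All of this stands, and it limits the point to two rules and a small expected effect on AE counts.

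A reader might infer more, and the documents do not support it:

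- That safety findings in general are credited to the wrong treatment. The AE problem needs both an incomplete onset and treatment assigned from the imputed date.
- That an event worsening after a later dose is lost to that treatment. Protocol 7.4.1.2 has unfavourable changes in condition recorded as AEs, so a worsening can be entered with its own onset.
- That every misplaced event moves incidence by 8.3 points. That is the maximum.
- That the End of Trial table will have columns of four. That presumes grouping by last treatment, which the SAP does not state.

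A further fair objection concerns the obvious remedy. Anchoring onset to the period in which the event was reported would itself misplace some events. The 144 h sample falls 6 days after tepotinib. At minimum washout the next Day -1 falls 9 days after that dose if B or C follows, or 13 days if A follows. That leaves 2 or 6 days without a visit (days 7-8 or 7-12). An event from that gap, first mentioned at the next admission, belongs to the earlier period.

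**Conclusion.** The point holds for two specific rules. First, the onset imputation can place a Period 2 or 3 event under an earlier treatment. This rests on reading the start of trial treatment as the first dose in the trial, which fits the SAP's practice of naming the period when it means one, and on treatment being taken from the imputed date. The documents give no rate of incomplete dates. The effect is probably small, with a ceiling of 8.3 points per event when a treatment has 12 subjects.

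Second, a by-treatment display of End of Trial versus Screening cannot be interpreted. This needs no missing data. The defect is a contrast that cannot be attributed to one treatment, not an attribution that the SAP states wrongly.

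Both affect descriptive safety tables only. This is a worthwhile clarification, not a threat to the trial's main result.

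**What to change.** Amend the SAP before database lock:

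1. **Assignment (15.1).** Assign each TEAE to the treatment of the period in which it began. A period runs from its first drug administration to the first drug administration of the next period.
2. **Imputation (15.1).** Set an incomplete onset to the first drug administration of the period in which the known date parts, the resolution date and the visit records show that it began, capped at the resolution date. Keep an event first reported on Day -1 of a later period in the preceding period. Flag cases that cannot be resolved.
3. **Shift tables (15.3).** Present End of Trial versus Screening overall only. Keep the by-treatment display for the within-period discharge versus predose shift.

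The cost is a few SAP sentences and minor programming. No new data are needed.
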